**Table 2 Study Milestones**

Milestone	Planned date a	Actual/revised date
Interim Report 2	15 months after protocol endorsement (expected Oct 2022)	Jan 2023 (planned revised date)
Interim Report 3	21 months after protocol endorsement (expected Apr 2023)	Will be replaced with a progress report for the same period
Amended protocol endorsement by EMA/MHRA	TBD (expected Jan 2023)	
Progress Report 2 d	April 2023	This will replace Interim Report 3
Feasibility assessment report for comparative analysis	June 2023	
Final report of study results	27 months after protocol endorsement (expected Oct 2023)	June 2024 (planned, revised)

a The schedule is dependent on protocol endorsement date, data extraction in each data source, and contracts with the research team.

b Start of data collection: the date from which information on the first study subject is first recorded in the study data set or, in the case of secondary use of data, the date from which data extraction starts [IR Art 37(1)]. Simple counts in a database to support the development of the study protocol, eg, to inform the sample size and statistical precision of the study, are not part of this definition.

c End of data collection: the date from which the analytical data set is completely available [IR Art 37(2)]. Analytical data set: the minimum set of data required to perform the statistical analyses leading to the results for the primary objective(s) of the study.

d After communication with EMA (10 Aug 2022), the PRAC Rapporteur team proposed to replace Interim Report 3 (April 2023) with a progress report covering the same period.

EMA, European Medicines Agency; EU PAS, European Union electronic Register of Post-Authorisation Studies; MHRA, Medicines and Healthcare products Regulatory Agency; PRAC, Pharmacovigilance Risk Assessment Committee (of the EMA); TBD, to be determined.

Timing of the interim reports will be driven by dates of protocol endorsement by the European Medicines Agency (EMA), contracting between research institutions, a minimum time of data accrual and the needed documentation of analytical instructions, data extraction, analysis, and reporting. Content of the progress report and interim reports is described in Section 9.7.12.

## 7. RATIONALE AND BACKGROUND

The novel coronavirus SARS-CoV-2 (severe acute respiratory syndrome coronavirus 2), the cause of coronavirus disease 2019 (COVID-19), has led to a global pandemic. AZD1222 (called Vaxzevria® in Europe) is a vaccine that was developed to prevent COVID-19.

Coronaviruses are enveloped viruses with positive-sense single-stranded RNA genomes. The spike glycoprotein is a coronavirus surface protein involved in receptor binding and mediating

virus entry into host cells during infection (Li 2016). AZD1222 is a recombinant replication-defective chimpanzee adenovirus expressing the SARS-CoV-2 spike glycoprotein. Development of AZD1222 was initiated by the University of Oxford with subsequent transfer of development activities to the Sponsor.

On 30 December 2020, the UK Medicines and Healthcare products Regulatory Agency (MHRA) provided authorisation for emergency supply of AZD1222, and on 29 January 2021, the European Commission granted conditional marketing authorisation for the vaccine. Now known as COVID-19 Vaccine AstraZeneca, the vaccine in both jurisdictions is indicated for active immunisation to prevent COVID-19 caused by SARS-CoV-2, in individuals aged 18 years and older. The vaccination course consists of 2 separate intramuscular injections. The second dose should be administered between 4 and 12 weeks (28 to 84 days) after the first dose. Since May 2022, a booster dose may be given at least 3 months after the second dose. A booster dose of AZD1222 can also be given to adults who have had 2 doses of an authorised mRNA COVID-19 vaccine but is beyond the scope of this study. At the national level, public health bodies may issue official recommendations, taking into account emerging effectiveness data and the limited safety data.

The protocol was prepared based on the most current version of the European Union (EU) risk management plans (RMPs) under review by EMA/PRAC, which, at the time of protocol approval, is EU RMP Version 5.0. Based on this version of the EU RMP, the safety concerns for AZD1222 include nervous system disorders (including immune-mediated neurological conditions), vaccine-associated enhanced disease (including vaccine-associated enhanced respiratory disease), thrombocytopenia with associated bleeding, anaphylaxis, thrombosis, and “thrombosis with thrombocytopenia syndrome” (TTS). Areas of missing information include use of AZD1222 in pregnant or breastfeeding women, use in immunocompromised individuals, use in frail individuals with comorbidities, use in those with autoimmune or inflammatory disorders, and interactions with other vaccines and long-term safety.

This post-authorisation safety study (PASS), which is required in AstraZeneca’s approved EU RMP, will evaluate the incidence and relative risk of safety concerns and AESIs, as defined in the approved EU RMP, following immunisation in the real-world setting. A retrospective, longitudinal cohort study will be conducted using existing secondary automated electronic health data sources to address these safety concerns in the general population as well as within special populations for which there is missing information. Self-controlled risk interval (SCRI) analyses will also be implemented for specific AESIs for which the risk interval for vaccine-associated effects is known.

## 8. RESEARCH QUESTION AND OBJECTIVES

The primary study objectives are as follows:

- 1 To describe the baseline characteristics (eg, demographics, medical history) of all subjects in the *matched population*
- 2 To describe, among subjects who receive a first dose of AZD1222 (ie, in the *all AZD1222 vaccinated first dose population*), the timing and type of second dose of any COVID-19 vaccine (AZD1222 or other) over the study period
- 3 To describe the incidence rates (IRs) of prespecified AESIs in subjects who received at least 1 dose of AZD1222 in the *matched population* and subjects who did not receive any vaccination against COVID-19 (concurrent unvaccinated comparators) in the *matched population*
- 4 To estimate the relative and absolute risk of prespecified AESIs in subjects who received at least 1 dose of AZD1222 compared with concurrent unvaccinated comparators in the matched populations, using a retrospective cohort design and an SCRI design

Secondary objectives are as follows:

- 1 To describe the baseline characteristics (eg, demographics, medical history) of all subjects in the matched population among the specific populations considered to have missing information (Section 9.2.1.2)
- 2 To describe, among subjects who receive a first dose of AZD1222, (ie, in the *all AZD1222 vaccinated first dose population*), the timing and type of second dose of any COVID-19 vaccine (AZD1222 or other) over the study period among the specific populations considered to have missing information
- 3 To describe the IRs of prespecified AESIs in subjects who received at least 1 dose of AZD1222 in the *matched population* and subjects who did not receive any vaccination against COVID-19 (concurrent unvaccinated comparators) in the *matched population*, among the specific populations considered to have missing information
- 4 To estimate the relative and absolute risk of prespecified AESIs in subjects who received at least 1 dose of AZD1222 compared with concurrent unvaccinated comparators in the matched populations, among the specific populations considered to have missing information, using a retrospective cohort design and an SCRI design

Exploratory objectives are as follows:

- 1 To describe the IRs of prespecified AESIs in subjects who received an mRNA vaccine against COVID-19 (either Comirnaty or Spikevax) (active comparators) and in subjects

- from the pre-pandemic period (2017-2018) (historical comparators) in the matched population
- 2 To estimate the relative and absolute risk of prespecified AESIs in subjects who received at least 1 dose of AZD1222 in the matched population compared with historical comparators in the matched population.
  - 3 To estimate the relative and absolute risk of prespecified AESIs in subjects who received 2 doses of AZD1222 in the matched population compared with subjects who received 2 doses of active comparator (Comirnaty or Spikevax as per homologous vaccination regimen) in the matched population.

No specific hypotheses will be tested during the study described in this protocol.

*Additional considerations (exploratory objective 3):*

In order to more robustly handle the known temporal variability of AESIs across the various vaccines (AZD1222, Comirnaty or Spikevax) and within vaccine by dose, the relative and absolute risk will be estimated only in a restricted study population considered homologous in terms of vaccine exposure and who received 2 doses as per recommended vaccine schedule.

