**Figure 1 Self-controlled Risk Interval Design**

Note: Example with a risk period of 42 days and a control period of 42 days.

ACCESS, vACCine Covid-19 monitoring readinESS; COVID-19, coronavirus disease 2019; T, time measured in days.

Source: “Safety evaluation of COVID-19 vaccines in electronic healthcare databases: a protocol template from the ACCESS project.”

The cohort study is proposed as the primary approach because, unlike the SCRI design, this approach can be used to study outcomes with gradual onset (eg, multiple sclerosis), long latency, and/or risk intervals that cannot be well defined (eg, chronic fatigue syndrome), and it also allows estimation of risk difference. On the other hand, the main strengths of the SCRI design are that it implicitly adjusts for time-invariant confounders and that it can still be used to estimate relative risk even if everyone is vaccinated during the study period. Moreover, in contrast to the cohort design, including only exposed individuals minimises exposure misclassification due to imperfect capture of vaccinations in secondary data sources.

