#### 9.2.1.1 Cohort Design: Study Population

##### 9.2.1.1.1 ALL AZD1222 VACCINATED POPULATION

The *all AZD1222 vaccinated population* will include all subjects vaccinated with at least 1 dose of AZD1222 during the study period. No other inclusion or exclusion criteria will be applied. For each AESI, subjects who had an event of a specific AESI (Table 3) during the clean look-back interval were excluded from the cohort included in the analysis for the specific AESI with which they had history, but not from the analysis cohorts for other AESIs.

The **index date** will be the date when a subject received the first AZD1222 dose within the study period. Subjects who received AZD1222 after another COVID-19 vaccine as a second or third dose only will also be included in this population.

This population will be included in the analysis to address primary objective 4 and secondary objective 4 of the study (SCRI design).

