### 9.2.1.2 Special Populations

In addition to the general study population, safety concerns will also be evaluated in prespecified subgroups for which information was deemed missing in the RMP.

- Women who are pregnant or breastfeeding
- Immunocompromised subjects
- Frail subjects with comorbidities (eg, chronic obstructive pulmonary disease, diabetes, chronic neurological disease, cardiovascular disorders)
- Subjects with autoimmune or inflammatory disorders
- Subjects who, at cohort entry, had recently received vaccines to prevent diseases other than COVID-19, such as pneumococcal infection, influenza, and shingles (herpes zoster).

Concepts to identify the special populations are listed in [Appendix C, Annex Table 3](#). Details on algorithms to identify each of these subgroups will be documented in a SAP.

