### 9.7.9 Subgroup Analyses

Subgroup analyses of special populations of interest (Section [9.2.1.2](#)) will be conducted using the analogous approaches used for the general study population described in Sections [9.7.1](#) (*Secondary Objective 1*), [9.7.2](#) (*Secondary Objective 2*), [9.7.6](#) (*Secondary Objective 3*); and [9.7.7](#) and [9.7.8](#) (*Secondary Objective 4*). No dose-specific analyses are planned for subgroups, given the expected limited precision of estimates.

Subgroup analyses may also be conducted based on age groupings.

No quantitative evaluations of effect modification are planned, however, for each AESI, forest plots will be generated for each subgroup and for the general population to facilitate visual comparison.

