## **Appendix C Additional Information**

**Annex Table 1 Covariates Proposed to Define the Study Population and Cohorts**

Related to AZD1222 vaccination
Date of dose 1
Date of dose 2
Number of doses
Timing between doses
Related to non-AZD1222 vaccines against COVID-19
Receipt of any SARS-CoV-2 vaccine other than AZD1222
Date of vaccination
Duration of available look-back period
Earliest date of data availability
Exclusion and censoring criteria
Latest date of data availability
For each AESI: dates of occurrence
Date of death

AESI, adverse event of special interest; COVID-19, coronavirus disease 2019; SAP, statistical analysis plan; SARS-CoV-2, severe acute respiratory syndrome coronavirus 2.

Note: A final list of covariates and their operational definitions will be specified in the SAP.

**Annex Table 2 Covariates Proposed to Define Subgroups of Interest Included as Missing Information in the EU RMPa**

To identify women who are pregnant or breastfeeding
Pregnancy status at cohort entry (algorithms including pregnancy outcomes such as miscarriage or live birth will be used to determine duration of pregnancy)
Breastfeeding status at cohort entry (as available, or measured by proxy, such as first 6 months postpartum)
To identify immunocompromised patients
Receipt of organ transplantation
Specific white cell haematological neoplasias (eg, chronic lymphocytic leukaemia, chronic myeloid leukaemia, multiple myeloma)
Human immunodeficiency virus (HIV) infection
Primary immunodeficiencies (eg, chronic granulomatous disease [CGD])
Recent or current use of immunosuppressive medications, eg, cytotoxic chemotherapy, biologic immunomodulatory therapies, methotrexate, chronic corticosteroid use
To identify autoimmune and inflammatory disorders
Rheumatoid arthritis
Polymyalgia rheumatica
Systemic lupus erythematosus
Crohn's disease and ulcerative colitis
Other autoimmune and connective tissue diseases (eg, primary biliary cholangitis, systemic sclerosis, psoriasis, vasculitis)
Neuroimmune conditions (eg, multiple sclerosis, myelitis, previous GBS)
To identify frail patients with comorbidities
Indicators of frailty
Dispensing of or reimbursement for durable medical equipment (eg, wheelchairs, home oxygen)
Residence in long-term facility or nursing home
Hip fracture
Palliative care
Metastatic cancer
Cachexia
Dementia
Pressure ulcers
Bladder incontinence

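### Secondary objective 4 applies the SCRI to two special populations defined by a passing state at vaccination, so its IRR can depart from 1 with no AZD1222 effect

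*Protocol*

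**What the plan says.** Section 8, secondary objective 4, asks for relative and absolute risk "among the specific populations considered to have missing information, using a retrospective cohort design and an SCRI design". Section 9.2.1.1.1 confirms that the all AZD1222 vaccinated population is used "to address primary objective 4 and secondary objective 4 of the study (SCRI design)". Section 9.7.9 says that the subgroup analyses "will be conducted using the analogous approaches used for the general study population", and it points to both the cohort methods (9.7.7) and the SCRI methods (9.7.8).

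Section 9.2.1.2 lists the five special populations. Two are states that end:
- "Women who are pregnant or breastfeeding"
- "Subjects who, at cohort entry, had recently received vaccines to prevent diseases other than COVID-19"

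Status is read once. Appendix C, Annex Table 2, has "Pregnancy status at cohort entry" and offers the first six months postpartum as a proxy for breastfeeding. Section 9.2.1.2 gives no length for a recent vaccine.

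Sections 9.1.2 and 9.2.3.2 place the control interval after the risk interval: in the Figure 1 example, 42 days at risk, a 7-day washout, then 42 control days. Section 9.1.2 notes that "the main strengths of the SCRI design are that it implicitly adjusts for time-invariant confounders". Section 9.7.8 allows time-varying confounders as covariates but does not require them, and leaves their definition and the analytic approach to the SAP.

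**The concern.** A self-controlled comparison needs the background rate to be the same in the two intervals, or the change to be modelled. Here the subgroup is selected because a possible risk factor is active at vaccination, and that factor tends to fade or change before the control interval starts. The suitability criteria in section 9.1.2 concern the AESI. None asks whether the background is steady in the subgroup.

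For the recent-vaccine subgroup, any effect of the other vaccine would be credited to AZD1222. Section 7 lists interactions with other vaccines as missing information, so this bias would look like the very finding the subgroup was set up to detect. Section 9.7.9 also plans forest plots beside the general population, where affected vaccinees are diluted. For pregnancy and breastfeeding, women move through gestation, delivery and the weeks after it between the two intervals.

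**Working it through.** **Plan's own figure.** The protocol gives no figure on this point. Its nearest SCRI figure (section 9.5) is 80% power at an IRR of 2 with about 70 events, half of the observation time exposed and alpha 5%. The signed-root likelihood-ratio formula, two-sided, gives 81.1% with 70 events, so it reproduces.

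**Inputs.** Risk interval days 1-42 and control interval days 50-91 (Figure 1 and section 9.2.3.2). State-specific rate ratios are assumptions. The calculations cover dose 1 with a complete control interval and no adjustment.

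**(a) Recent other vaccine.** Let it be given *d* days before AZD1222, with rate ratio *k* on its own days 1-42. That window ends on AZD1222 day 42 − *d*, always before day 50, so the control interval is untouched:

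null IRR = 1 + (*k* − 1)(42 − *d*)/42 for *d* < 42, and 1 otherwise.

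| *d* (days) | *k* = 1.5 | *k* = 2 |
|---|---|---|
| 0 | 1.50 | 2.00 |
| 14 | 1.33 | 1.67 |
| 28 | 1.17 | 1.33 |
| 42 or more | 1.00 | 1.00 |

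Now average over a definition of recent, with timing uniform over days 0 to *D* − 1:
- *D* = 30: mean of (42 − *d*)/42 = 27.5/42 = 0.655. Null IRR 1.65 (*k* = 2) or 1.33 (*k* = 1.5).
- *D* = 183: the terms for days 0-41 sum to 21.5, and 21.5/183 = 0.117. Null IRR 1.12 or 1.06.
- *D* = 365: 21.5/365 = 0.059. Null IRR 1.06 or 1.03.

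Window length matters. If both vaccines have a 14-day window, the terms sum to 7.5, and *D* = 30 with *k* = 2 gives 1 + 7.5/30 = 1.25.

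**(b) Pregnancy or breastfeeding, merged as planned.** Assume a rate of 1 in pregnancy, *R* in the first 42 days after delivery and *L* later. Women are spread uniformly over 280 gestation days and 183 postpartum days.

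Worked case, *R* = 5 and *L* = 1:
- Pregnant at index: expected early-postpartum days are 903/280 = 3.225 in the risk interval and 1,764/280 = 6.3 in the control interval. Rate sums are 42 + 4 × 3.225 = 54.9 and 42 + 4 × 6.3 = 67.2, ratio 0.82.
- Postpartum at index: 861/183 = 4.705 days and 0 days. Rate sums are 60.8 and 42, ratio 1.45.
- Merged: (280 × 54.9 + 183 × 60.8)/(280 × 67.2 + 183 × 42) = 1.00.
- With 75% postpartum: (0.25 × 54.9 + 0.75 × 60.8)/(0.25 × 67.2 + 0.75 × 42) = 1.23.

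The same sums with *L* from 0.3 to 1.0:

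| *R* | uniform mix | 75% postpartum |
|---|---|---|
| 2 | 1.00-1.10 | 1.06-1.29 |
| 5 | 1.00-1.07 | 1.23-1.56 |
| 10 | 1.00-1.05 | 1.44-1.84 |

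**Effect on intervals.** By the same power formula, a null IRR of 1.33 makes a nominal 95% CI exclude 1 in 9%, 22% and 53% of analyses with 20, 70 and 200 events. At 1.17 the figures are 5%, 9% and 19%.

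**The case against.** The strongest reply is that section 9.7.8, which section 9.7.9 carries into the subgroups, already allows time-varying confounders and assigns the detail to the SAP. That stands in part: a reader might infer that the protocol makes no provision for a changing background, and that would be wrong. But the provision is optional, and it cannot help when both vaccines are given on the same day with the same risk window. The two exposures then coincide and no covariate separates them. That limit comes from the design choice in the objective.

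Second, the size rests on assumptions. A shared risk window does not show that influenza, pneumococcal or shingles vaccines raise any of these AESIs, and the documents give no rates for pregnancy or the postpartum period. This stands. With a broad definition of recent the bias is small. Events after dose 2, to which a vaccine given before dose 1 adds little or nothing, would dilute it further.

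Third, splitting the pregnancy/breastfeeding subgroup gives alarming values: under the model above, 1.11 to 4.62 for postpartum women alone. A reader might take these as the bias in the planned analysis. The protocol plans one merged subgroup, and with a uniform mix the two halves largely cancel.

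Fourth, the SCRI is complementary, the cohort is primary, and section 9.7 avoids reading results by significance. This limits the consequence but does not make a biased point estimate interpretable.

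**Conclusion.** The point holds conditionally. In these two subgroups the SCRI IRR can depart from 1 with no AZD1222 effect, because self-control does not remove a background that changes between the intervals. A reader might infer that it must depart from 1. The documents do not support that: the state has to alter the rate of the particular AESI, and for a 42-day window the other vaccine has to fall within the preceding 42 days.

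For a recent other vaccine the direction is fixed by the sign of that vaccine's own effect. With an assumed rate ratio of 2, the null IRR runs from 2.0 (same day) through about 1.65, 1.12 and 1.06 (recent meaning 30, 183 or 365 days, uniform timing) to 1.0. For pregnancy or breastfeeding it is about 1.00-1.10 with a uniform mix and larger if most women are postpartum, and the documents do not give the mix. This should be corrected, but it does not undermine the primary cohort analysis.

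**What to change.** In secondary objective 4 and section 9.7.9, answer these two subgroups from the matched cohort, and bring section 9.2.1.1.1 into line. The cohort is already planned and matches comparators on special-population status. It does not match on gestational phase or on days since the other vaccine, so it reduces the problem without removing it fully.

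If the SCRI is kept in these subgroups:
- change 'may' to 'will' in section 9.7.8 for them;
- exclude subjects given the other vaccine on the same day as AZD1222;
- model the other vaccine's own risk interval as a second time-varying exposure, which works only where the dates differ;
- include pregnancy/postpartum phase as a time-varying term.

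The text should not describe the other three populations as stable. Annex Table 2 defines them partly by current cytotoxic chemotherapy and palliative care, which can also change over weeks.

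The cost is protocol and SAP wording, plus interval splitting on data already held if the SCRI stays. The downside is no SCRI estimate, or a less precise one, in two small subgroups, and with it the loss there of the SCRI's control of fixed confounders.

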## **9. RESEARCH METHODS**

### **9.1 Study Design**

Using information from several healthcare databases, this observational population-based multinational study will primarily employ a retrospective cohort design to compare subjects who have received at least one dose of AZD1222 with subjects who have not yet received any COVID-19 vaccine (concurrent unvaccinated comparators), subjects who received an mRNA vaccine (either Comirnaty or Spikevax) (active comparators – 2 doses), and subjects enrolled in the study data sources any time during the pre-pandemic period (ie, 2017-2018) (historical comparators) for the occurrence of AESIs. Secondly, it will employ an SCRI design for a subset of AESIs that are appropriate for this approach, as described in Section 9.1.2.

This study, which will be conducted in the VAC4EU (Vaccine monitoring Collaboration for Europe, <https://vac4eu.org/>) research environment, will use a common protocol across all study sites, a common data model (CDM) and common analytics. It will use case definitions developed by the vACCine Covid-19 monitoring readinESS (ACCESS) project, which was funded by the EMA to prepare a European infrastructure to monitor COVID-19 vaccines. This protocol is adapted from a template developed by the ACCESS project entitled “Safety evaluation of COVID-19 vaccines in electronic healthcare databases” ([ACCESS Project 2020](#)).

The study will be conducted using information collected in electronic healthcare data sources in Europe. The proposed data sources are the Clinical Practice Research Datalink (CPRD) in

the UK, the Valencia Health System Integrated Database (VID) and the Information System for Research in Primary Care (SIDIAP) database in Spain, the Regional Health Agency of Tuscany (ARS Toscana) in Italy, and PHARMO Database Network (PHARMO) in the Netherlands. These data sources were selected because they are able to capture the data elements needed to conduct this study, cover areas where AZD1222 use was expected, have been used in prior studies of vaccine safety, and appear to have reasonably short data lags, which is necessary to conduct interim analyses (Willame et al 2021) (Section 9.4). The study period will run from the introduction of AZD1222 in each country in early 2021 for 24 months for the evaluation of all AESIs.

